5.1.4. Pharmacokinetic (PK) Population

The PK Population includes all subjects in the MITT Population with at least 1 serum PK sample collected post-dose.

5.1.5. Safety Population

The Safety Population includes all subjects who receive any amount of study drug and have at least 1 post-treatment safety assessment.

5.2. Study Endpoints

5.2.1. Microbiological and Clinical Assessments

ETA specimens will be collected for culture during Screening/Enrollment to determine randomization eligibility, including identification of heavy *S. aureus* colonization. Additional respiratory specimens may be collected for culture throughout the Monitoring Period or at Early Termination (if applicable) if clinically indicated according to routine standard of care.

If, as part of routine standard of care, additional respiratory and/or other microbiological specimens are collected for culture during the study, results will be documented within the eCRF. As described within the study lab manual, bacterial isolates recovered from these specimens that are deemed pathogens by the Investigator (if retained and available at the study site local microbiology laboratory) will be sent to the central microbiology laboratory for confirmation of pathogen identification (all isolates) and susceptibility testing (*S. aureus* isolates only).

During the Monitoring Period, a diagnosis of *S. aureus* pneumonia will be determined if subjects have *S. aureus* identified at any level from an adequate respiratory specimen by the local microbiology laboratory or central microbiology laboratory if the local microbiological sample was either not done, cultured improperly, or no growth. For a diagnosis of *S. aureus* pneumonia, the collection of an adequate respiratory specimen culture that is positive for *S. aureus* must occur within ± 2 days from the time of the

development of clinical signs and symptoms of pneumonia or chest imaging results indicative of pneumonia:

- A respiratory specimen obtained by BAL, non-bronchoscopic BAL, or protected specimen brush will be considered an adequate respiratory specimen; or
- For extubated subjects, an adequate expectorated/induced sputum specimen is defined as one that does not have either 10 squamous epithelial cells or 25 PMNs/100× field will also be an adequate respiratory specimen; and
- For both intubated and extubated subjects, adequate respiratory specimens will undergo either semi-quantitative or quantitative culture in accordance with the local laboratory’s standard procedure.

Subjects will be assessed daily throughout the Monitoring Period for the following clinical signs and symptoms:

Clinical Signs and Symptoms

Mechanically Ventilated Subjects	Non-Mechanically Ventilated Subjects

 • Cough, • Rales, • Dullness on percussion,* • Bronchial breath sounds, • Egophony,* • Need for suctioning, • Need for ventilator support, and • Fever ³38°C (³100.4°F). 	
 • Cough, • Rales, • Dullness on percussion,* • Bronchial breath sounds, • Egophony,* • Dyspnea, • Tachypnea, • Respiratory rate, • Hypoxemia, and • Fever ³38°C (³100.4°F).
*If routinely performed.	

A diagnosis of pneumonia will be determined by the Investigator based on their clinical expertise and experience.

Each pneumonia diagnosis will be categorized programmatically as HABP or VABP using the definitions below. Programmatically determined assignments as HABP and VABP will be evaluated for confirmation or Sponsor Override as applicable by the Review Group. The final categorizations will be performed in a blinded fashion and prior to final database lock and unblinding. After the Review Group’s review, the decision to override a programmatic determination will be finalized and documented. The reasons for Sponsor Overrides will be included in the analysis datasets.

Definition of Hospital-Acquired and Ventilator-Associated Bacterial Pneumonia

Indication	Definition
HABP	
 · A chest image showing new or progressive infiltrates suggestive of pneumonia; · Subject has been off of mechanical ventilation via an endotracheal or nasotracheal tube for >48 hours; · At least ONE of the following: 
 ○ Has been hospitalized for >48 hours; or ○ Developed clinical signs and symptoms within 7 days following hospital discharge; · At least ONE of the following: 
 ○ New onset or worsening pulmonary signs/symptoms such as cough, dyspnea, tachypnea (e.g., respiratory rate >25 breaths per minute), expectorated sputum production, or the requirement for mechanical ventilation (if subject is not already ventilated); ○ Need for acute changes in ventilator support to enhance oxygenation or to the amount of PEEP; or ○ New onset of suctioned respiratory secretions; AND · At least ONE of the following clinical signs/symptoms: 
 ○ Temperature >38°C or <35°C; ○ WBC count ³ 10,000 cell/mm³ or ≤4500 cell/mm³; or ○ >15% immature neutrophils (bands) on peripheral blood smear.
VABP	
 · A chest image showing new or progressive infiltrates suggestive of pneumonia; · Subject has received mechanical ventilation via an endotracheal or nasotracheal tube for ³ 48 hours; · At least ONE of the following: 
 · Currently receiving mechanical ventilation via an endotracheal or nasotracheal tube; or · Discontinued receiving mechanical ventilation via an endotracheal or nasotracheal tube within the last 48 hours (i.e. 48 hours); · At least ONE of the following: 
 ○ New onset or worsening pulmonary signs/symptoms such as cough, dyspnea, tachypnea (e.g., respiratory rate >25 breaths per minute), expectorated sputum production, or the requirement for mechanical ventilation (if subject is not already ventilated); ○ Need for acute changes in ventilator support to enhance oxygenation or to the amount of PEEP; or ○ New onset of suctioned respiratory secretions; AND · At least ONE of the following clinical signs/symptoms: 
 ○ Temperature >38°C or <35°C, ○ WBC count ³ 10,000 cell/mm³ or ≤4500 cell/mm³, or ○ >15% immature neutrophils (bands) on peripheral blood smear.

HABP = hospital-acquired bacterial pneumonia; PEEP = positive end-expiratory pressure; VABP = ventilator-associated bacterial pneumonia; WBC = white blood cell.
	

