## 7.4 Microbiological and Clinical Assessments

### 7.4.1 Microbiological Assessment

ETA specimens will be collected for culture during Screening/Enrollment to determine the degree of *S. aureus* colonization. Additional respiratory specimens may be collected for culture throughout the Monitoring Period or Early Termination (if applicable) if clinically indicated according to standard of care.

If, as part of routine standard of care, additional respiratory and/or other microbiological specimens are collected for culture during the study, results will be documented within the eCRF. As fully described within the study lab manual, bacterial isolates recovered from these specimens that are deemed pathogens by the Investigator (if retained and available at the study site local microbiology laboratory) will be sent to a central microbiology laboratory for confirmation of pathogen identification (all isolates) and susceptibility testing (*S. aureus* isolates only).

During the Monitoring Period, a diagnosis of *S. aureus* pneumonia will be determined if subjects have *S. aureus* identified from an adequate respiratory specimen (Section 7.4.1) and clinical signs and symptoms of pneumonia. For a diagnosis of *S. aureus* pneumonia, clinical signs and symptoms must occur  $\pm 2$  days from the time of collection of an adequate respiratory specimen culture that is positive for *S. aureus* (Section 7.4.2).

- For intubated subjects, a respiratory specimen obtained by BAL, non-bronchoscopic BAL, or protected specimen brush will be considered an adequate respiratory specimen; or
- For extubated subjects, an adequate expectorated/induced sputum specimen is defined as  $<10$  squamous epithelial cells and  $>25$  PMNs/100 $\times$  field; and
- For both intubated and extubated subjects, adequate respiratory specimens will undergo either semi-quantitative or quantitative culture in accordance with the local laboratory's standard procedure.

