5.2.2. Sponsor-Defined Outcome of *S. aureus* Pneumonia

Sponsor-Defined Outcome (SDO) of *S. aureus* pneumonia will be determined programmatically based on the data and the manual review conducted at Review Meetings per the POP.

Each randomized subject will be evaluated for the occurrence of *S. aureus* pneumonia between Randomization and up to, but not including, Day 22. In order to assign a SDO, the following assessments will be made based on available data:

1. Microbiological Assessment
2. Chest Imaging Assessment
3. Clinical Assessments
 - a. Respiratory
 - b. Signs and Symptoms
4. Operational Assessments

There will be 2 SDO definitions for data analysis: SDO1 and SDO2. The 2 definitions will need to satisfy the 4 assessments above and differ only on the clinical assessments. SDO1 will meet either respiratory OR signs and symptoms requirements while SDO2 will meet both respiratory AND signs and symptoms requirements.

The individual assessments for each randomized subject will be collapsed to assign an SDO1/SDO2 of Yes, No, Indeterminate (i.e. insufficient data to assign a SDO of Yes or No), or Censored (i.e. subject died prior to the Day 22 assessment) based on the mutually exclusive, hierarchical rules specified in the POP.

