5.2.4. Primary Efficacy Endpoint

The primary efficacy endpoint is whether the subject has developed an SDO1 of *S. aureus* pneumonia up to, but not including, Day 22. The summary measure for efficacy is the proportion of subjects in the MITT Population who develop an SDO1 of *S. aureus* pneumonia up to, but not including, Day 22.

Analyses of the primary efficacy endpoint will also be performed separately for the ITT and PP Populations.

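### SAP 5.2.1 lets chest imaging alone satisfy the ±2-day link to the positive culture, where the protocol requires clinical signs; no window for the clinical part of SDO1 is stated and the change is not declared

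*SAP*

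**What the plan says.** **Protocol 7.4.1** (the synopsis has the same rule) fixes the link between culture and illness. For a diagnosis of *S. aureus* "pneumonia, clinical signs and symptoms must occur" within ±2 "days from the time of collection of an adequate respiratory specimen culture that is positive for" the organism. No imaging alternative is offered, and no window is set for the chest image.

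**SAP 5.2.1** turns the rule around and widens it. Collection of the positive specimen "must occur within ± 2 days from the time of the" "development of clinical signs and symptoms of pneumonia or chest imaging results indicative of pneumonia".

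**SAP 5.2.4** then builds the primary endpoint on the Sponsor-Defined Outcome: "The primary efficacy endpoint is whether the subject has developed an SDO1 of" *S. aureus* pneumonia before Day 22.

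**SAP 5.2.2** requires microbiological, imaging, clinical and operational assessments for that outcome. On the clinical part it says: "SDO1 will meet either respiratory OR signs and symptoms requirements while SDO2 will meet both respiratory AND signs and symptoms requirements". The only time limit stated there is the outer one: "Each randomized subject will be evaluated for the occurrence of *S. aureus* pneumonia between Randomization and up to, but not including, Day 22". The detailed assignment rules, and a manual review, are left to the POP.

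**SAP Section 9** lists analyses added since the protocol. The changed timing rule is not among them.

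**The concern.** The timing link is what makes a culture, an infiltrate and a clinical picture into one pneumonia. It carries more weight than usual here. Every subject in the MITT Population is heavily colonized with *S. aureus* at entry, and SAP 5.2.1 accepts the organism at any level of growth, so a positive culture discriminates only weakly. Coincidence with clinical illness supplies much of the specificity.

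Under the SAP wording, once the image lies close to the culture, nothing stated in the SAP says when the clinical findings must have occurred, other than between randomization and Day 21. Because SDO1 accepts either respiratory findings or signs and symptoms, the gap applies to both kinds of finding.

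If unrelated findings complete events at the same rate in both arms, the observed difference shrinks and power falls. The false-positive rate is not affected, because equal true rates stay equal.

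**Working it through.** **1. The two rules side by side**

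| Record | Protocol 7.4.1 window | SAP 5.2.1 window |
|---|---|---|
| Signs, image and culture all on Day 6 | met | met |
| Image and culture on Day 16; clinical findings only on Day 3 | not met | met, through the image |
| Image on Day 2; signs and culture on Day 18 | met | met |

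Only the second record separates the documents. It passes the SAP's timing rule. Whether it becomes an SDO1 event depends on how the Day 3 findings are treated, and SAP 5.2.2 does not say. The third record shows no loosening, because the protocol sets no imaging window either.

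**2. The plan's own sample size**

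Inputs from SAP Section 6: 25% v 12.5%, two-sided 0.05, 80% power. The pooled normal approximation gives

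n = [1.960·√(2·p̄(1−p̄)) + 0.842·√(p₁(1−p₁) + p₂(1−p₂))]² / (p₁−p₂)²

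With p̄ = 0.1875: n = (1.960 × 0.552 + 0.842 × 0.545)² / 0.125² = 151.9, so 152 per arm. Power at 152 is 0.800, and 304/(1−0.14) gives 354 randomized. The plan's figures reproduce and are not in dispute.

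**3. Sensitivity to false events (assumption, not from the documents)**

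Let a fraction f of true non-cases in each arm be counted as events. Then p′ = p + f(1−p), and the difference becomes (1−f) × 12.5 points.

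For f = 5%: p₁′ = 0.25 + 0.05 × 0.75 = 0.2875 and p₂′ = 0.125 + 0.05 × 0.875 = 0.1688.

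| f | Placebo v ASN100 | Power at 152 per arm | n per arm for 80% |
|---|---|---|---|
| 0 | 25.0% v 12.5% | 0.80 | 152 |
| 1% | 25.8% v 13.4% | 0.78 | 161 |
| 2% | 26.5% v 14.3% | 0.76 | 169 |
| 5% | 28.8% v 16.9% | 0.70 | 195 |

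**4. What a given f would require**

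A false event of this kind also needs an infiltrate and a positive adequate specimen within 2 days of each other. Assume an unrelated qualifying finding arises with daily chance 5%, 10% or 20%, independently across days. The chance of at least one is 1−(1−p)⁵ = 23%, 41%, 67% in a 5-day window and 1−(1−p)²¹ = 66%, 89%, 99% over 21 days. The added pass probability is the difference: about 43%, 48%, 32%. Dividing f by these values gives the share of non-cases who would need such an image–culture pair:

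- f = 1%: about 2–3%
- f = 2%: about 4–6%
- f = 5%: about 10–16%

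The documents give no figure for this share.

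**The case against.** The strongest reply is that SAP 5.2.1 governs only when the specimen must be collected. The primary event is SDO1, assigned by POP rules with manual review, and population and outcome decisions are made blinded. The POP may already set a clinical window. This stands as a limit on the consequence. A reader might infer that signs from another week do complete primary events; the documents do not show that, only that the SAP states nothing to prevent it. The reply does not remove the conflict, because the SAP states a timing rule of its own and it differs from the protocol's.

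Other replies have force:

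- The discrepant record in the table is atypical. Protocol Table 1 counts need for suctioning and need for ventilator support as signs in ventilated subjects, so someone still ventilated around Day 16 could meet the protocol window too. The record clearly differs only for a subject off the ventilator, or if those items are not counted.
- Protocol 9.7 requires monitoring-period imaging when respiratory signs appear, so most images will lie near signs.
- The SAP dates signs from their development, where the protocol says only that they occur. The SAP's signs branch may therefore be the narrower of the two.
- Added events need not be false. An infiltrate with *S. aureus* in an adequate specimen within 2 days may be genuine pneumonia.
- SDO2 and the Kaplan-Meier analyses that use the Review Meeting's judgement of causation (SAP 7.11.2) give partial protection. They are supportive only, and SDO2 has no stated window either.

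**Conclusion.** The point holds as a discrepancy in the definition of the primary event. The SAP's stated timing rule is looser than the protocol's, the clinical component of SDO1 and SDO2 has no stated window, and Section 9 is silent. The consequence is conditional: remote clinical findings could complete a primary event unless the POP prevents it.

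The size is unknown. Under the assumption of equal false-event fractions in both arms, 1–2% of non-cases costs 2 to 4 points of power and 5% costs about 10. A reader might infer a much larger loss, for example power of 0.60 at a 10% false-event fraction. On the assumed daily rates above, that would need about 21–31% of non-cases to have a paired infiltrate and positive culture, and nothing in the documents supports it. Even the 5% case needs 10–16%. These figures are sensitivities, not forecasts.

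**What to change.** Before unblinding, as SAP Section 3 allows:

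1. Reconcile Protocol 7.4.1 and SAP 5.2.1 by restoring in the SAP the requirement that the qualifying clinical findings occur within ±2 days of collection of the positive adequate specimen.
2. State that this applies to the clinical component of both SDO1 and SDO2, and align the POP.
3. If the imaging alternative is intended, declare it in Section 9 with its reason, and report the primary analysis under the protocol window as a sensitivity analysis.

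Requiring the culture to be within ±2 days of both the signs and the image goes further than this discrepancy supports. It would add an imaging window found in neither document.

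The cost is a change of wording in the SAP and POP and one programming condition. A few true cases with delayed signs or cultures may have to go to blinded review.

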## 4 SELECTION AND WITHDRAWAL OF SUBJECTS

### 4.1 Inclusion Criteria

Subjects must meet all of the following criteria at the Screening and Randomization Visits in order to be eligible for randomization into the study:

1. Subject, legally authorized representative (LAR), or CIP (if applicable) has provided written informed consent;
2. Subject is  $\geq 18$  years of age at the time of enrollment;
3. Subject is currently hospitalized and is mechanically ventilated endotracheally (i.e., orotracheal or nasotracheal) and, in the Investigator's opinion, will require ongoing ventilator support for at least 48 hours;

NOTE: Subjects with a tracheostomy at the time of enrollment are not eligible. After enrollment, conversion to tracheostomy is permitted per standard of care.

4. Female subjects must not be pregnant or lactating. Female subjects of childbearing potential must have a documented negative pregnancy test at the Screening Visit. Female subjects may be enrolled on the basis of a negative urine pregnancy test, pending the result of a negative serum pregnancy test prior to randomization; and
5. Female subjects of childbearing potential and non-surgically sterile male subjects who are sexually active must agree to use an approved highly effective form of contraception from the time of informed consent until 165 days post-dose. Approved forms of contraception include hormonal intrauterine devices, hormonal contraceptives (oral birth control pill, depo, patch, or injectable) together with supplementary double barrier methods such as condoms or diaphragms with spermicidal gel or foam.

NOTE: The following categories define women who are NOT considered to be of childbearing potential:

- Premenopausal female with 1 of the following:
  - Documented hysterectomy,
  - Documented bilateral salpingectomy, or
  - Documented bilateral oophorectomy, or
- Postmenopausal female, defined as having amenorrhea for at least 12 months without an alternative medical cause.

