#### **4.3 Randomization Criteria**

Following the Screening Visit, eligible subjects who meet all of the inclusion criteria and none of the exclusion criteria will be screened daily (while mechanically ventilated) for up to 8 days via quantitative or semi-quantitative culture of an ETA to identify those subjects who are heavily colonized with *S. aureus* (see Section 3.1).

Screening for heavy *S. aureus* colonization by ETA culture will continue on Day 11 and Day 14 provided the subject remains mechanically ventilated, for a total Screening Period of up to 14 days. Additional ETA screening may occur on Days 9, 10, 12, and 13 at the discretion of the Investigator and providing the subject remains mechanically ventilated.

Once an enrolled subject has an ETA culture reported positive for heavy *S. aureus* colonization and meets all of the inclusion and none of the exclusion criteria, they are eligible for randomization. If they are not randomized on this occasion according to the protocol, they are no longer eligible for continued ETA sampling and randomization, and will be discontinued from the study; however, if subjects are extubated and subsequently re-intubated/mechanically ventilated, they are eligible for re-screening as a new subject enrollment. Subjects who were previously randomized are not eligible to be re-consented and re-screened.

At the time of randomization, if a subject's screening ETA culture also shows heavy colonization of a Gram-negative organism (i.e., heavy co-colonization of both Gram-positive and Gram-negative organisms), the subject will not be randomized into the study.

NOTE: Randomization should not be delayed while waiting for Gram-negative results if heavy colonization with *S. aureus* has been confirmed.

At the Randomization Visit, subjects must meet all of the following requirements to be randomized into the study:

1. Subject continues to meet all of the inclusion criteria and none of the exclusion criteria required at the Screening Visit;

NOTE: Subjects who undergo tracheostomy after enrollment are still eligible for randomization, provided they remain mechanically ventilated (see criterion 3 below).

2. Subject is heavily colonized with *S. aureus* as determined by either quantitative or semi-quantitative culture of an ETA (see Section 3.1);

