7.12. Subgroup Analyses

The following subgroups will be used for subgroup analyses for the primary efficacy endpoint in the MITT and PP Populations, i.e. whether the subject has or doesn't have of *S. aureus* pneumonia up to, but not including, Day 22 for both SDO1 and SDO2

populations. The exploratory efficacy endpoints, the incidence of all pneumonias, and the incidence of other non-*S. aureus* pneumonias up to, but not including, Day 22 in the MITT and PP Populations, will also undergo the following subgroup analyses.

- Corrected Randomization stratification (Receipt or Non-Receipt of concomitant anti-staphylococcal antibiotics at the time of randomization that are potentially active against *S. aureus* pneumonia.)
- Type of ICU (e.g., SICU, MICU, Neuro ICU, Trauma ICU)
- Type of mechanical ventilation (Tracheotomy or Non-Tracheotomy) at Randomization
- Length of stay in the intensive care unit (ICU) post-treatment (<5, 5-12, >12-22, and >22 days)
- Duration of mechanical ventilation before randomization (48 vs. >48 hours)
- Baseline MRSA/MSSA from qualifying ETA culture
- Pneumonia MRSA/MSSA
- Reason for mechanical ventilation
- BMI categories: <25, 25-<30, 30-<35, and 35
- Age: <50, 50-<65, and >65
- WBC $\times 10^9/L$ at Baseline: <1, 1 to <2.5, 2.5 to <5, 5 to <10, and >10
- Platelet count $\times 10^9/L$ at Baseline: <50, 50 to <150; 150 to <400, and > 400
- Change in platelet count from Baseline: decrease by 50% or greater, or an increase by 50% or greater
- Male vs. female
- Smoker vs. non-smoker
- History of COPD vs. non-COPD
- History of alcohol use vs. no history of alcohol use
- Hospital readmission within 30 days after discharge
- Qualifying ETA and Screening ETA cultures: *S. aureus* only vs. co-colonized *S. aureus* and any Gram-negative at any time before randomization vs. co-colonized *S. aureus* and any other organism at any time before randomization
- Procalcitonin at Baseline for those who develop pneumonia vs. those who don't develop pneumonia: <median vs. median
- Qualifying ETA culture: *S. aureus* 3+ vs. 4+ vs. Heavy
- Cardiac events yes/no from receipt of study drug to Day 90 or early termination
- Multi organ failure yes/no from receipt of study drug to Day 90 or early termination

- Acute kidney injury defined by an absolute increase in serum creatinine of 0.3 mg/dL or a 50% increase (*viz.*, 0.3 mg/dL increase if baseline = 0.6 mg/dL and 50% increase if baseline is = 0.6 mg/dL) within 48 hours from receipt of study drug

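### The SAP's HABP/VABP rule does not count tracheostomy ventilation, so a subject still ventilated that way more than 48 hours after leaving the oral or nasal tube is programmed as HABP, not VABP

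*SAP*

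**What the plan says.** The split is mechanical. SAP Section 5.2.1 states: "Each pneumonia diagnosis will be categorized programmatically as HABP or VABP using the definitions below". The blinded Review Group then confirms or overrides each assignment before database lock.

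Three lines in those definitions concern the airway:

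- HABP: "Subject has been off of mechanical ventilation via an endotracheal or nasotracheal tube for >48 hours".
- VABP, first alternative: "Currently receiving mechanical ventilation via an endotracheal or nasotracheal tube".
- VABP, second alternative: "Discontinued receiving mechanical ventilation via an endotracheal or nasotracheal tube within the last 48 hours".

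VABP also needs at least 48 hours of ventilation by such a tube. Tracheostomy appears in none of these lines.

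The trial nevertheless expects tracheostomy ventilation. Protocol Section 4.1 requires that the subject "is mechanically ventilated endotracheally (i.e., orotracheal or nasotracheal"), bars a tracheostomy at enrollment and permits conversion afterwards. Protocol Section 4.3 adds: "Subjects who undergo tracheostomy after enrollment are still eligible for randomization, provided they remain mechanically ventilated". SAP Section 7.12 has a subgroup for "Type of mechanical ventilation (Tracheotomy or Non-Tracheotomy) at Randomization".

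The VABP definition in Protocol Table 2 has the 48-hour exposure line but no condition that tube ventilation be current or recent. Its HABP definition has no airway line at all. The current, recent and off-ventilation conditions are therefore additions made in the SAP.

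**The concern.** A subject converted to tracheostomy and still on the ventilator is no longer on an oral or nasal tube. Once 48 hours have passed since that tube was removed, both VABP alternatives fail and the HABP airway line is met, although ventilation never stopped.

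Nothing else in the HABP definition screens the subject out. An inpatient meets the 48-hour hospitalization line, and changes in ventilator support or new suctioned secretions count toward HABP as well as VABP.

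The incidence of VABP and of post-extubation HABP by arm are two stated exploratory objectives (SAP Section 4.1.3). A rule that takes ventilated subjects out of the VABP count works against the distinction those objectives rest on.

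**Working it through.** The plan states no figure on this point, so the check is to apply the airway lines to test cases, with the imaging and clinical criteria taken as met.

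Let *E* be total hours of oral or nasal tube ventilation, and *T* the hours since that ventilation ended (0 if current).

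- SAP HABP airway line: *T* > 48.
- SAP VABP airway lines: *E* ≥ 48 and *T* ≤ 48.
- Protocol VABP airway line: *E* ≥ 48.
- Any-airway rule: the same as the SAP, but tracheostomy ventilation counts toward *E* and sets *T* to 0 while it continues.

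| Case | *E* | *T* | SAP as written | Meets protocol VABP? | Any-airway rule |
|---|---|---|---|---|---|
| On oral/nasal tube | 120 | 0 | VABP | yes | VABP |
| Tracheostomy, still ventilated | 120 | 24 | VABP | yes | VABP |
| Tracheostomy, still ventilated | 120 | 48 | VABP | yes | VABP |
| Tracheostomy, still ventilated | 120 | 49 | **HABP** | yes | VABP |
| Tracheostomy, still ventilated | 120 | 240 | **HABP** | yes | VABP |
| Extubated, off ventilator | 120 | 24 | VABP | yes | VABP |
| Extubated, off ventilator | 120 | 72 | HABP | yes | HABP |
| Tracheostomy, still ventilated | 30 | 24 | **neither** | no | VABP |

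The *E* and *T* values are chosen for illustration; *E* and *T* in the table count oral or nasal tube hours only.

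Three things follow.

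1. For a subject ventilated throughout, the programmed category changes from VABP to HABP when *T* passes 48 hours, with no change in ventilation.
2. Protocol Table 2 would still class the 49- and 240-hour cases as VABP, because *E* ≥ 48. They would meet protocol HABP too, since that definition has no airway line. The loss of VABP status comes from the SAP's added conditions.
3. A subject with a short oral or nasal tube period and a recent conversion fits neither SAP category.

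The next step is the endpoint. SAP Sections 5.2.6 and 7.11.4 report HABP arising more than 48 hours after extubation, in extubated subjects. Neither document says whether conversion to tracheostomy is extubation. If it is, the 49- and 240-hour cases enter the HABP proportion while the subject is on a ventilator. If it is not, they are programmed HABP, filtered out of the HABP endpoint, and absent from VABP. VABP is short by those cases under either reading.

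**The case against.** **The program's output is not final.** Review is blinded, precedes lock and records reasons for override, and a ventilated subject labelled HABP should be noticed. This stands as a limit: the documents do not show that the final data would be misclassified. But the SAP gives the Review Group no tracheostomy criterion, and a reviewer who applies the written definition would confirm HABP. The Population and Outcome Plan, where the procedures sit, was not supplied and may cover the case.

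**The word endotracheal might include a tracheostomy tube.** The SAP does not define it, and pairing it with nasotracheal would be redundant if the protocol's gloss carried over. Against this, Protocol Section 4.1 explains the term as oral or nasal and treats tracheostomy separately in its note. The narrower reading is the better supported one, and a programmer should not have to choose.

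**The added SAP lines have a purpose.** They separate two categories that overlap in Protocol Table 2. That is true, and they should be kept and extended, not removed.

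**Stronger readings a reader might infer.** One is that HABP is overcounted. The restriction to extubated subjects means that is only one of two possible outcomes. Another is a case count. The design rates give 152 × 0.25 + 152 × 0.125 = 57 expected *S. aureus* pneumonias in evaluable subjects, and one could multiply by an assumed tracheostomy fraction. That base omits other pneumonias, which the split also covers, and no document supplies the fraction. A third is bias between arms. That would need tracheostomy use or ventilator duration to differ by arm, which the documents do not show.

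**Conclusion.** The concern holds for the rule as written. A subject still ventilated through a tracheostomy more than 48 hours after leaving the oral or nasal tube is programmed as HABP and not VABP unless overridden. VABP is therefore undercounted, and the case is either counted as HABP or lost from both endpoints.

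This rests on three assumptions: that endotracheal carries the protocol's meaning, that the imaging and clinical criteria are met, and that the Population and Outcome Plan has no rule correcting it.

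The reach is limited. The HABP and VABP proportions are exploratory and summarized descriptively (SAP Section 7.11.4). A reader might infer that the primary result is at risk, but the documents do not support that. The primary endpoint is the sponsor-defined outcome SDO1, built from microbiological, imaging, clinical and operational assessments (SAP Section 5.2.2), and the HABP/VABP split is not among them. Incidence of all pneumonias is also unaffected, because under the SAP the Investigator's diagnosis comes before the split. The number of affected cases cannot be estimated from the documents. It should be corrected before unblinding, but it does not threaten the main analysis.

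**What to change.** - In the airway lines of both SAP definitions, count ventilation by an endotracheal, nasotracheal or tracheostomy tube. HABP then requires being off all invasive ventilation for more than 48 hours. Apply the same wording to the VABP 48-hour exposure line; otherwise the short-tube case in the table remains in neither category.
- In SAP Sections 5.2.6 and 7.11.4, state that conversion to tracheostomy while still ventilated is not extubation. The SAP's VABP objective in Section 4.1.3 refers to intubated subjects and needs the same clarification.
- Carry the wording into the Population and Outcome Plan and the derivation program before unblinding.
- List the departure from Protocol Table 2 in SAP Section 9, which does not mention the airway conditions already added. The exposure line currently matches the protocol, so extending it is a further difference to record there.

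The cost is a few phrases and a small change to one derivation. Ventilator device status is already in the schedule of procedures, and SAP Section 3 allows modification before unblinding. Nothing in the care of subjects changes.
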